7.1.2. Summary Measure

The posterior predictive probability of RV dysfunction in a hypothetical individual for a pre-determined “pre-dose” Ang II value,

The posterior predictive probability of RV dysfunction in a hypothetical individual for a pre-determined “post-dose” Ang II value, and

The difference between the above two probabilities.

7.1.3. Population of Interest

The primary pharmacodynamic analyses will be based on the Evaluable population, unless otherwise specified.

7.1.4. Strategy for Intercurrent (Post-Randomization) Events

Intercurrent events which may lead to missing data for all variables (such as death) would not impact the primary analysis since the planned modelling assumes no lag between RAS peptide concentrations and effect on RV dysfunction (i.e. RAS concentrations on day 1 are not used to predict RV dysfunction on day 2 and if death occurs between day 1 and day 2 this will not impact the planned modelling).

Intercurrent events such as taking a non-permitted con med may require exclusion of post medication data if the con med had the potential to confound the true relationship between RAS peptide and RV dysfunction.

Intercurrent events that result in missing data for one or more of the variables required for the primary analysis (e.g. ECHO view not suitable, lost RAS sample) will result in the exclusion of the impacted timepoint as there is not sufficient information to postulate a suitable imputation model.

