10.3. Statistical Analyses

10.3.1. Pharmacodynamic Analyses

Endpoint	Statistical Analysis Methods
Primary	
The association of Ang II with RV function (measured by PASP and RV size ratio) will be modelled using a Bayesian repeated measures mixed effects linear regression model, where PASP and RV size ratio are joint response variables, and including subject as a random effect and log(Ang II), age and sex as fixed effects. The model will be used to make a probabilistic prediction of PASP and RV size ratio for two reference values of Ang II, and hence an estimate for the probability of RV dysfunction (defined as PASP > 40 mmHg or RV size ratio > 0.6, following Boissier 2013) for the two given Ang II levels will be obtained using mean values for the other continuous covariates and averaging over all levels of class effects for categorical covariates.
 
The above modelling may use a modified Ang II value (modification based on the corresponding Ang(1-7) result to account for potential inhibitory interactions); details to be provided in the reporting and analysis plan (RAP).
 
The primary analysis will use the Evaluable population.

Secondary	
Association of Ang(1-7) with RV function (measured by PASP and RV size ratio) and of Ang II/Ang(1-7) with RV function (measured by PASP and RV size ratio) will both be modelled as per the primary analysis described above. These analyses will be done using the Evaluable population.
 
A model including both Ang II and Ang(1-7) as co-predictors of RV function may also be built, to explore the relationship between RV function and the envisaged dual action of angiotensin converting enzyme (ACE)2 effecting a reduction in Ang II together with a simultaneous increase in Ang(1-7).
 
Incidence of PCD and ACP during the three days of the study period and prevalence of pre-existing PCD/ ACP on entry to the study will be reported with 95% confidence intervals. This analysis will be done using the Completed population (which includes a clause to include participants who have an onset of PCD/ ACP but are subsequently withdrawn from the study before all three days' worth of data are collected without withdrawing consent).
 
The distribution of PASP, RV size ratio and other measurements of RV function in mechanically ventilated participants will be assessed via a combination of descriptive summary tables and outputs from the statistical modelling.

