4. ANALYSIS POPULATIONS

Population ¹	Definition / Criteria	Analyses Evaluated
Screened	All participants who have been screened.	
• To aid construction of Consort diagram in any publication
Enrolled	All participants who had passed screening and who had appropriate informed consent (via any of the processes described in the protocol).	
• Summary of Subject Status and Reason for Study Withdrawal• Summary of Study Populations• Summary of Exclusions from the

Population ¹	Definition / Criteria	Analyses Evaluated
		Safety/Completed/ Evaluable Populations
Safety	All participants for whom at least one echocardiograph and/or blood sample has been taken, and who did not retrospectively withdraw the consent.	
 • Study population (excl. specific tables mentioned below) • Safety
Evaluable	All participants for whom PASP, RV size ratio, Ang II and Ang(1-7) data have been recorded for at least one study time point, and who did not retrospectively withdraw the consent (and who still had at least one study time point of data remaining after accounting for any prohibited concomitant medications (for example but not limited to renin inhibitors, ARBs or ACE inhibitors) – See Section 10.1.1).	
 • Pharmacodynamic/ Biomarker (excl. disease diagnosis status)
Evaluable with Prohibited Con Meds	All participants in the Evaluable population plus any participants who were excluded from the Evaluable population because of prohibited concomitant medications (for example but not limited to renin inhibitors, ARBs or ACE inhibitors)	
 • Sensitivity for Primary analysis (conditional on number of prohibited con meds)
Completed ²	All participants for whom PASP, RV size ratio, Ang II, and Ang(1-7) data have been recorded for all three study days.	
 • Disease diagnosis status
At Risk	
For the purpose of evaluating ACP/PCD and ARDS incidence rates the participants who satisfy
 
1) PASP and RV size ratio recorded for all three study days (regardless of the Ang II and Ang(1-7) status)
 
and/or
 
2) databased ACP/PCD and/or ARDS assessment during the study period (even if they do not have three days' worth of study assessments for the above echo outcomes)
 
provided consent is not withdrawn.
	
 • Disease diagnosis status

NOTES :

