7. PHARMACODYNAMIC AND BIOMARKER ANALYSES

7.1. Primary Pharmacodynamic/Biomarker Analyses

7.1.1. Endpoint / Variables

The following variables may be included in the statistical model:

- Independent variable of interest:
 - Ang II on Study Days 1, 2 and 3 (after any imputations)
- Dependent (bivariate) variable of interest:
 - PASP on Study Days 1, 2 and 3
 - RV size ratio on Study Days 1, 2 and 3
- Potential covariates (to be explored, order listed indicates expected importance):
 - Centre
 - Age at screening
 - Sex
 - Use of vasopressors on Study Days 1, 2 and 3
 - PEEP on Study Days 1, 2 and 3
 - Proning status on Study Days 1, 2 and 3
 - BMI at screening
 - Concurrent use of inhaled nitric oxide on Study Days 1, 2 and 3
 - Mean airway pressure on Study Days 1, 2 and 3
 - Tidal Volume on Study Days 1, 2 and 3
 - ECMO on Study Days 1, 2 and 3
 - ECCO2R on Study Days 1, 2 and 3
 - SAPS II at screening
 - PaO₂/FiO₂ on Study Days 1, 2 and 3

Additionally, the presence/absence of paradoxical septal motion on Study Days 1, 2 and 3 may be assessed on an informal visual basis.

Note: Since the study was terminated early there may not be sufficient information in the collected data to explore covariate analyses and the covariate exploration process may not take place at all.

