7.1.5. Statistical Analyses / Methods

The purpose of the primary analysis is to evaluate the association of biomarkers of the Renin Angiotensin System (RAS), specifically Ang II but secondarily Ang(1-7) with measures of RV function (specifically PASP and RV size ratio in the primary model, and also paradoxical septal motion on a more informal visual basis), whilst taking into account any observable variables that may confound the relationship between the two concepts.

RV function will be measured using PASP and RV size ratio. The general principle underlying all the analyses of RV function and RAS peptide biomarkers will be:

- model the joint distribution of PASP and RV size ratio as a function of the RAS peptide(s) in question (together with confounding variables also included as covariates),
- choose reference values of the RAS peptide(s) in question and estimate a posterior distribution of PASP and RV size ratio for those given values, and
- use the posterior distribution to determine the probability of RV dysfunction (for a future individual participant), defined (following the definition of moderate/severe pulmonary circulatory disease given in [Boissier, 2013](#)) as:
 - PASP > 40 mmHg
 - RV size ratio > 0.6

The advantage of this method is that all the information on the continuous scales of PASP and RV size ratio is maintained throughout the modelling process, and that dichotomising

participants into binary categories takes place at the end after the modelling has been done.

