7.2. Secondary Efficacy Analyses

7.2.1. Endpoint / Variables

The variables to be included in the secondary pharmacodynamic analysis are the same as for the primary pharmacodynamic analysis, with the addition of the following independent variables:

- Ang(1-7) on Study Days 1, 2 and 3
- (Optionally) Ang(1-5) on Study Days 1, 2 and 3 (if the correlation between Ang(1-7) and Ang(1-5) values is not too high – otherwise the analysis would not be expected to add additional insights/value)
- Note: The planned modelling using similar techniques to the primary analysis for the Ang II/Ang(1-7) response on Study Days 1, 2 and 3 will not be attempted.

Incidence rates would be assessed across

- i) the entire study (the outcome taking the value of the worst case observed) and
- ii) on an individual visit basis (Note: Screening and Day 1 data would be combined and labelled as Day 1; the worst case outcome used in any combination)

The following rates would be assessed

- Incidence rates of ARDS diagnosis
- Incidence rates of PCD or ACP (any right ventricular dysfunction; regardless of PCD or ACP severity level)
- Incidence rates of PCD (Moderate PCD (not severe enough to qualify as ACP))
- Incidence rates of Non-severe ACP
- Incidence rates Severe ACP

Additionally, the worst case PCD/ACP diagnosis across the study would be combined with the ARDS diagnosis to form the following categories

- ARDS and No PCD or ACP
- ARDS and PCD
- ARDS and Non-Severe ACP
- ARDS and Severe ACP

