10. APPENDICES

10.1. Appendix 1: Protocol Deviation Management and Definitions for Evaluable Population

10.1.1. Exclusions from Evaluable Population

Subjects with major/important protocol deviations will be considered for exclusion from Evaluable Population. The Protocol Deviation Management Plan (PDMP) will be used to determine major/important protocol deviations that will lead to exclusion from the Evaluable Population (Note: In the event the PDMP retains the template text / default terminology which refers to “per protocol population” it would be interpreted as the “Evaluable population” for study 205821).

In addition, a subject meeting any of the following criteria will be excluded from the Evaluable population (or if more applicable, only the relevant timepoint(s) excluded):

Number	Exclusion Description
01	
Participants whose day 1, day 2 and day 3 samples were all lost or for whom the post sample processing was unable to produce evaluable results would be excluded from the evaluable population
 
If a single day (or two days) are impacted by the above reason(s) then the participant shall remain in the evaluable population, but the impacted time points would be removed from the analysis.

02	
If a single day (or two days) are impacted by the ECHO results that are later deemed of insufficient quality (e.g. this may be discovered by independent review/adjudication of source notes) then those data points would be removed from the analysis (but the participant would remain in the evaluable population). If all of the day 1, day 2 and day 3 ECHO results are impacted in this way then the participant would be removed from the evaluable population.

03	
If the participant takes a prohibited concomitant medication that, in the opinion of the GSK medical monitor, may confound / interfere with the estimation of the true relationship between RAS peptides and an endpoint then any post con-med observations would be removed from the corresponding analysis.

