3	Numerical entry	Missing (.)	Missing (.)	No result
4	Numerical entry	Numerical entry	<TPG + RAP>	<TPG + RAP>

Note: All PASP values in analysis and reporting datasets and consequent tables, listings and figures will be re-derived by stats and programming using the algorithms in Table 7.

PASP values are also automatically derived within the eCRF form and are supplied in the data management transfer of the CV dataset under the CVTSTCD of “AH001”. However, it has been noted in test data transfers that the auto calculation does not always derive correct results due to the complexities of the data source combinations (e.g. Participant PPD Day 1 had a TPG from the TOE method but an estimated RAP from the TTE method but the eCRF autocalculation incorrectly supplied a missing PASP value). Therefore there is a need to programmatically re-drive PASP and as a consequence there will be additional records in ARDATA versions of the CV dataset compared to the SI version (CVTSTCD = AH001CAL).

To facilitate sensitivity analyses regarding the frequency/reason of “missing” PASP values an additional variable may be created in ARDATA datasets (as required) that tracks the inputs to the PASP calculation (see [Table 8](#)). This tracking variable would not need to be displayed in the listing of echocardiogram endpoints.

Table 8 Additional variable/result to track the derived PASP inputs (assigned a CVTSTCD = AH001src)

AH001src value	TPG source used in derivation of PASP (see Table 5)	RAP source used in derivation of PASP (See Table 6)
1	Missing (".")	Missing (".")
2	Missing (".")	TTE
3	Missing (".")	TOE
4	Missing (".")	Measured
5	TTE	Missing (".")
6	TTE	TTE
7	TTE	TOE
8	TTE	Measured
9	TOE	Missing (".")
10	TOE	TTE
11	TOE	TOE
12	TOE	Measured

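### The primary Ang II model discards a visit with a measured RV size ratio whenever PASP is missing, although the planned joint model can use it

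*SAP*

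**What the plan says.** SAP 7.1.1 lists "PASP on Study Days 1, 2 and 3" and RV size ratio on the same days as one bivariate response, with Ang II as the predictor. SAP 7.1.5 sets the principle: "model the joint distribution of PASP and RV size ratio as a function of the RAS peptide(s) in question". The model is a Bayesian bivariate normal regression whose covariance is a Kronecker product of a between-outcome matrix (Sigma) and an AR(1) matrix over visits (Tigma).

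For missing data, SAP 7.1.4 gives an unsuitable echo view and a lost RAS sample as examples. It says that either "will result in the exclusion of the impacted timepoint as there is not sufficient information to postulate a suitable imputation model".

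SAP 10.6.6 Table 7 makes PASP missing if either the transtricuspid gradient or right atrial pressure is missing. RV size ratio is selected separately (Tables 2 and 3), so it can be present without PASP. The only provision for missing PASP is that "an additional variable may be created in ARDATA datasets (as required) that tracks the inputs to the PASP calculation". That variable is optional, and no analysis that restores the visits is attached to it.

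The Evaluable population (SAP 4) is "All participants for whom PASP, RV size ratio, Ang II and Ang(1-7) data have been recorded for at least one study time point", so a participant who never has a PASP leaves the primary analysis altogether. For echo results of insufficient quality on one or two days, SAP 10.1.1 item 02 says "then those data points would be removed from the analysis (but the participant would remain in the evaluable population".

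**The concern.** The SAP applies one rule to two different problems. If Ang II is missing, the predictor is missing. The model gives it no distribution, so the stated reason for exclusion is fair. If PASP is missing, the quantity lost is one of two modelled outcomes. A visit with only RV size ratio contributes its marginal normal term to the planned likelihood, and no separate imputation model has to be postulated.

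Deleting such visits loses information on the RV size ratio slope. It also introduces bias if the chance of obtaining PASP depends on RV size ratio, because the retained visits are then selected on an outcome. The results at stake are the SAP 7.1.2 summary measures: the two predicted probabilities of RV dysfunction and their difference. The study stopped early, so measured visits are scarce. Protocol 9.5.3 foresees gradients that cannot be measured, but its acceleration-time substitute serves diagnosis and not this model.

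Two lesser points sit alongside:

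- Evaluable requires at least one Ang(1-7) value, yet Ang(1-7) enters only the secondary models, whose variables "are the same as for the primary pharmacodynamic analysis, with the addition of the following independent variables". This acts per participant and probably has a small effect.
- SAP 7.1.4 removes the timepoint, while 10.1.1 item 02 removes data points. It is unclear whether a poor PASP alone also removes that visit's RV size ratio.

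**Working it through.** **Inputs from the documents** (Protocol 12.5.1 and 12.5.4): log Ang II has mean 2.78 and SD 1.74; PASP has mean 38 and SD 8 mmHg; RV size ratio has mean 0.61 and SD 0.15; the PASP–RV correlation is 0.5. RV dysfunction is PASP > 40 or RV size ratio > 0.6. SAP 7.1.5 sets the Ang II references at 30 and 8 pg/mL.

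**Assumed:** all missingness rates and mechanisms; N = 30; AR(1) correlation 0.6 and Ang II visit correlation 0.7 in the three-visit simulations.

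**Step 1. The plan's own figure.** Re-running the protocol simulation (N = 50, both correlations 0.6, references 55.4 and 7.1, no missing data, 2,000 studies) gave 75.9% success and a mean difference of 34.3 points. The protocol states 74.7% and 33.9. All nine scenarios of Table 1a came within 2 points.

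**Step 2. True contrast at the SAP references, correlations 0.3/0.3.**
- Slopes per log unit: PASP 0.3 × 8 / 1.74 = 1.379; RV 0.3 × 0.15 / 1.74 = 0.0259.
- Means at 30 pg/mL (ln 30 = 3.401): PASP 38 + 1.379 × 0.621 = 38.86; RV 0.626. At 8 pg/mL (ln 8 = 2.079): 37.03; 0.592.
- Residual SDs: 8√(1 − 0.09) = 7.63; 0.15√(1 − 0.09) = 0.143. Residual correlation: (0.5 − 0.09)/(1 − 0.09) = 0.451.
- P = 1 − P(PASP ≤ 40 and RV ≤ 0.6) = 68.9% and 59.1%, a contrast of 9.8 points. With correlations 0.6/0.6 the contrast is 23.6.

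**Step 3. Large-sample bias** (600,000 draws per scenario). Deletion is the bivariate regression on complete visits. Keeping uses the factorised likelihood: RV ratio given Ang II on all visits, and PASP given RV ratio and Ang II where PASP is observed. Missingness is logistic, slope 1–2 per SD, 20–40% missing.

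| PASP observed more often when | Correlations | True contrast | Deletion | RV ratio kept |
|---|---|---|---|---|
| RV ratio high | 0.3/0.3 | 9.8 | 8.7 to 5.9 | 9.7–9.8 |
| RV ratio high | 0.6/0.6 | 23.6 | 21.6 to 15.9 | 23.6 |
| RV ratio low | 0.3/0.3 | 9.8 | 9.7 to 9.1 | 9.8 |
| PASP itself high | 0.3/0.3 | 9.8 | 8.9 to 6.6 | 9.4 to 8.2 |

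An independent repeat agreed to about 0.1 point. The contrast alone understates the damage:
- Row 1: the predictions under deletion rise from 69%/59% to between 74%/66% and 85%/79%.
- Row 3: they fall to between 64%/54% and 52%/43%, with the RV slope at 0.69–0.90 of its true value.
- Row 4: keeping the RV ratio still leaves 71%/62% to 77%/69%. Lowering the imputed PASP by 4–8 mmHg returns contrasts of about 9.4–9.9.
- Missingness depending only on Ang II gives no bias under either method.

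**Step 4. Precision when PASP is missing completely at random** (N = 30, correlations 0.3/0.3; SD of the contrast in points, deletion vs kept).

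| Missing | One visit | Three visits, Kronecker covariance |
|---|---|---|
| 10% | 5.9 vs 5.6 | 3.2 vs 3.1 |
| 20% | 5.9 vs 5.4 | 3.4 vs 3.2 |
| 40% | 7.6 vs 5.8 | 4.0 vs 3.3 |

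The three-visit column uses 1,500 studies with known covariance. REML fits (400 studies each) gave 3.3 vs 3.3, 3.8 vs 3.5 and 3.8 vs 3.2, with visible Monte Carlo noise, and 4.3 vs 3.4 if 40% of participants never have a PASP. In a separate three-visit calculation (N = 50, correlations 0.6/0.6, visit autocorrelation 0.6 for outcomes and Ang II), deletion inflates the standard error of the RV slope by about 6%, 12%, 20% and 43% at 10%, 20%, 30% and 50% missing. The PASP slope is almost unaffected.

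**Step 5. Bias with three visits** (REML, 40% missing, PASP observed more often at high RV ratio). Slope 1: deletion 8.3 (RMSE 4.1) vs kept 9.9 (3.4). Slope 2: 6.5 (4.7) vs 9.7 (3.4).

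**The case against.** The strongest objection is that no effect is documented. Neither document gives a rate of missing PASP or links it to RV size ratio, so every bias figure rests on an assumed mechanism. Some mechanisms do no harm, such as missingness that depends only on Ang II. With three visits and random missingness the loss is slight until missingness is high. This stands, and it is why the size is given only as a range.

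The decision weight is also limited. The study was terminated, the interim analyses with the 15% and 30% rules were cancelled, and no formal hypothesis is tested. That stands too, but the predicted probabilities remain the reported primary result.

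The fit is fragile. SAP 7.1.5 records convergence trouble, and treating missing PASP as an unknown adds to the load. If PASP is missing because of its own value, keeping the visit removes only part of the bias. Both points are fair. They argue for convergence checks and a sensitivity analysis, not for deletion, which did no better on the predicted probabilities in any mechanism examined.

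Transoesophageal back-up and the TTE/TOE/right atrial pressure selection tables will recover some PASP values. They reduce the number of affected visits but leave the rule unchanged. Finally, Protocol 10.2 itself defines Evaluable by all four measures, so the change is more than a wording edit. The SAP has, however, already modified the protocol's Evaluable and Completed definitions.

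**Conclusion.** The concern holds. The exclusion rule is explicit, its stated reason does not apply to a missing outcome, and nothing else in the SAP brings the visits back. Under completely random missingness the cost is precision: negligible to small at 10–20% missing with three visits, and clearer at 40%. If PASP is obtained more often at a high RV size ratio, deletion takes about 1 to 4 points off a 9.8-point contrast (9.8 − 8.7 = 1.1; 9.8 − 5.9 = 3.9) and about 2 to 8 off a 23.6-point contrast (23.6 − 21.6 = 2.0; 23.6 − 15.9 = 7.7). Keeping the RV size ratio removes that bias. If missingness depends on PASP itself, the gain is partial.

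These sizes rest on the protocol's planning distribution and on assumed rates, mechanisms and sample size; the actual effect cannot be determined from the documents. The protocol's Table 1 assumed complete data and is not in question. The change should be made, though the plan is not invalid without it.

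**What to change.** 1. In SAP 7.1.4, fit the primary model to every visit with Ang II and at least one of PASP and RV size ratio. Treat the missing outcome as an unknown in the MCMC, keeping the full Sigma–Tigma covariance. Restrict the exclusion rule to a missing Ang II or to both outcomes missing.
2. Keep the complete-visit analysis as a sensitivity analysis.
3. Make the PASP source variable (AH001src) mandatory, and report the number of visits without PASP by RV size ratio and Ang II.
4. Add one missing-not-at-random sensitivity analysis, for example shifting imputed PASP over a pre-specified range in mmHg.
5. Require Ang(1-7) only for models that use it. That would include a primary model that, as Protocol 10.3.1 allows, "may use a modified Ang II value (modification based on the corresponding Ang(1-7) result".
6. Reconcile 7.1.4 with 10.1.1 item 02 on whether one poor outcome removes the whole visit.
7. Declare the altered Evaluable definition in SAP 2.1, since Protocol 10.2 and 10.3.1 fix the population.

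The cost is SAP wording, modest programming and extra convergence checking. The covariate dataset in SAP 10.6.10 already keeps visits with either outcome. The remaining weakness is reliance on missing at random given RV size ratio and Ang II, which item 4 is there to probe.
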